Visit 7 (subject dependent) Subjects will be assessed by medical history, neurological tests (FARS, Timed 25 foot walk (T25W), Timed 1 and 6 minute walks, Timed up and go (TUG), Berg Balance scale (BBS), 9 hole peg test (9HPT), PedsQL, ADL score and ataxia disability scale), biochemical tests (frataxin level, platelet metabolic biomarkers), and physiological testing (CrCEST, MEP). Data will be collected over a one day visit.

Data will be analyzed by [name] and collaborators. No subject visits occur during this time.

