4.7 Primary and Secondary Endpoints

The primary goal of this study is to gather long-term serial quantitative clinical data using the measures validated during the three years of the study.

Aims 1: The primary endpoint (s) are the change in each of the clinical measures over time. The rate of change of each of these will be compared for responsiveness to change (SD of change/mean change).

Aim 2: Biochemical measures: The rate of change of frataxin and each platelet biomarker will be determined as primary endpoints. The rate of change over time will be determined to define which measures are most sensitive to disease progression.

Aim 3: Anatomical measures: The primary endpoints are the post exercise recovery time, Tau, for CrCest and the MEP size for MEP testing. The rate of change over time will be determined to define which measures are most sensitive to disease progression.

The secondary analyses are:

The rate of change of each measure the (neurological measures, biochemical measures and anatomic measures) as a function of age, GAA repeat length and sex, as determined by linear regression models

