4.8 Statistical Methods

Aim 1: Results will be summarized with standard descriptive statistics using parametric or non-parametric methods, as appropriate given the variable distributions. Each of the parameters tested here have been abnormal in FRDA patients previously, including children. However, the specific features of how they behave in large pediatric cohorts is unclear. Thus, the most important analyses will be how the tests behave over time and how they reflect disease severity. Data for test-retest for the first 5 subjects at the primary site will be evaluated by determining the coefficient of variation over the tests. This will be performed immediately after study initiation as a separate analysis to confirm that the initial protocols have sufficient reproducibility to be useful. Full data collection will then proceed. Data from measures that were repeated (timed walks, TUG, CCFS tests) will be analyzed as means of the repeated tests and test retest features between trials. CCFS values will be analyzed as each hand separately (dominant vs non dominant) and hands together. Each test will be assessed in regression or mixed linear models accounting for age, sex and GAA repeat length. In addition the change over time will be established as well as the reproducibility of that change.

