Aim 2: Results will be summarized with standard descriptive statistics using parametric or non-parametric methods, as appropriate given the variable distributions. In this biochemical aim, the major analysis will examine the relationship of frataxin levels and downstream biomarkers with disease progression. This will be performed in 2 ways. First using cross sectional data, we will construct mixed linear models that allow the assessment of their relationship of marker values (frataxin, 13C metabolite levels, Apo A1) to age, GAA repeat length and sex. Secondly, we will assess the change in values over time both in absolute value and percent change to understand the overall meaning of results. In addition, the change over time will be examined in relation to age, sex, and GAA repeat length in linear models. We will also examine the levels of each marker at baseline with the change in clinical measures from aim 1. This will allow us to understand the degree to which clinical change reflects individual biochemical events and whether clinical and biochemical events correlate temporally. This analysis will be supplemented by analysis assessing whether the change in levels of the biomarkers predicts clinical change.

Aim 3. Each of the measures here (MEP, CrCEST) has differentiated FRDA subjects from controls in previous studies. For this proposal though, the crucial analyses should ascertain the relationship between physiological values from CrCEST and MEP and disease status from clinical measures. Results will be summarized with standard descriptive statistics using parametric or non-parametric methods, as appropriate given the variable distributions. In cross sectional analyses, results from each of the outcome measures (frataxin levels, platelet metabolic markers, ApoA-1, and recovery time from CrCEST) will

be used as dependent variables in multiple linear regression models or mixed models examining the independent effects of age, GAA repeat length and sex as dependent variables. This will allow us to define the degree to which each outcome marker is predicted by genetic severity (GAA repeat length), disease progression (age) or both. We will also directly correlate results between MEP and CrCEST to ascertain the degree to which they reflect the same construct (FRDA disease progression). Finally, we will examine correlations and regression modelling between physiological results and clinical measures (Aim 1) and frataxin levels (Aim 2)

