4.9 Sample Size and Power

The sample size of main parts of the study is dictated by previous studies and by practicality. Previous power calculations suggest that even using even well-defined clinical measures, the sample size for therapeutic trials will be more than 100 subjects, even using selected cohorts (9-13). However, the tests performed in the present study generally show robust differences between FRDA subjects and controls, and should provide more sensitive measures of disease if they retain sufficient fidelity in children. A sample size of 110 subjects should allow us to assess the independent effects of age, sex and genetic severity (GAA length) on measure results, facilitating a true understanding of the degree they can be used in children. One hundred subjects is also practically the upper limit of intervention studies in rare disease, and thus is appropriate for this study. In the present, study subjects will return every year for MEP and CrCEST, and every six months for clinical testing and blood tests through 36 months. MEP and CrCEST will have smaller samples size (30 and 12 respectively) as they are more precise but more labor intensive tests. Total duration for each subject is approximately 3-4 years, and initial recruitment will occur over a 2 year period. In the present study the goal is to define how each of the tests change over time in children with FRDA, and the factors (age, GAA length) that predict such changes. Each marker has been differentiated from control values previously; however, here control subjects will be used only if needed to confirm the differences, to provide a context and to be sure that tests perform similarly in all sites as a quality control measure.

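### The plan names linear regression, with no weighting, for the predictors of rate of change; on its plain reading this loses precision when children have short follow-up, and one random-slope model per measure would avoid that.

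*Combined protocol and SAP*

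**What the plan says.** Section 4.7 makes change over time the primary endpoint of each aim. Its secondary analyses take the rate of change of the neurological, biochemical and anatomical measures "as a function of age, GAA repeat length and sex, as determined by linear regression models". Section 4.8 says the same for Aim 2: "the change over time will be examined in relation to age, sex, and GAA repeat length in linear models".

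Mixed models appear in section 4.8 in three places:
- Aim 1: "Each test will be assessed in regression or mixed linear models accounting for age, sex and GAA repeat length". Change over time follows in a separate sentence that names no model.
- Aim 2: "First using cross sectional data, we will construct mixed linear models", for marker values rather than their change.
- Aim 3: results will "be used as dependent variables in multiple linear regression models or mixed models", under cross-sectional analyses.

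The plan does not say how a child's rate is computed, whether rates are weighted, what follow-up a child needs, or how missing visits are handled.

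Section 4.9 states "A sample size of 110 subjects should allow us to assess the independent effects of age, sex and genetic severity", and describes the factors that predict change as part of the study's goal. It gives no SD or dropout rate. MEP has 30 children and CrCEST 12. Section 3.1.2 dates visits at 0, 6, 12, 18, 24 and 36 months and adds a seventh whose timing depends on the child. Sections 3.1.5, 4.6 and 5.1 allow FACOMS data, including data from before enrolment, for co-enrolled children who agreed to sharing.

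**The concern.** A slope fitted to a short series is mostly measurement error. An ordinary regression of per-child slopes on age, sex and repeat length gives it the same weight as a well-determined three-year slope. The noise from a few short series can then account for a large part of the variance of the estimated effects.

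What is at stake is precision on a question that section 4.9 treats as central. In a rare disease with 110 children, that precision cannot easily be bought back by recruiting more. Children with one visit would also drop out of a slope regression altogether.

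**Working it through.** **Plan's own figure.** The 110 is set by earlier studies and practicality. No alpha, power, effect, SD or dropout is given, so there is nothing to reproduce.

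**Inputs.** Visit times come from section 3.1.2. Assumed: r = residual SD divided by the SD of true yearly slopes, from 0.5 to 2; the shares of children with short follow-up; and follow-up length unrelated to the predictors.

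**Step 1: error variance of one child's slope.** This is residual variance / Sxx, where Sxx is the sum of squared deviations of visit times in years.
- 0, 6, 12, 18, 24, 36 months: 16.5 − 6 × 1.333² = 5.83
- 0, 6, 12 months: 1.25 − 3 × 0.5² = 0.5
- 0, 6 months: 0.25 − 2 × 0.25² = 0.125
- 0, 36 months: 9 − 2 × 1.5² = 4.5

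Relative to the full schedule, the error variance is 5.83/0.125 = 46.7 times for 0 and 6 months, 5.83/0.5 = 11.7 times for 0, 6 and 12 months, and 5.83/4.5 = 1.3 times for 0 and 36 months. Time span matters more than visit count.

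**Step 2: loss in the regression.** In units of the true slope variance, an estimated slope has variance v = 1 + r²/Sxx. Unweighted regression has variance proportional to the arithmetic mean (AM) of v, and optimal weighting to the harmonic mean (HM). The loss is AM/HM.

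| r | v: 0–6 / 0–12 / full | 10% / 10% / 80% | 20% / 10% / 70% |
|---|---|---|---|
| 0.5 | 3.0 / 1.5 / 1.04 | 1.284/1.153 = 1.11 | 1.480/1.243 = 1.19 |
| 1 | 9 / 3 / 1.17 | 2.137/1.375 = 1.55 | 2.920/1.531 = 1.91 |
| 2 | 33 / 9 / 1.69 | 5.549/2.046 = 2.71 | 8.680/2.313 = 3.75 |

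**Step 3: other patterns.**
- Complete data: AM/HM = 1, no loss.
- 20% of children with only 0 and 36 months: efficiency (HM/AM) 1.00.
- 20% of visits missed at random: efficiency 1.00, 0.98 and 0.92 at r = 0.5, 1 and 2.

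**Step 4: earlier FACOMS data.** Suppose every child has one visit 12 months before baseline. Sxx becomes 10.5 (full), 2.19 (to 12 months) and 1.17 (to 6 months), so the largest ratio falls from 47 to 10.5/1.17 = 9. Putting these into step 2 for the 10%/10% mix, the loss is 1.03 at r = 1. At r = 2, v is 4.43, 2.83 and 1.38, and the loss is 1.831/1.569 = 1.17. For the 20%/10% mix the losses are 1.05 and 1.25.

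**Step 5: simulation check.** 110 children, 600 runs per setting, no earlier data, an assumed effect of 0.3 slope SDs per SD of the predictor, two-sided 5%. The mixed model was given the true variance components, which is a best case.

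| Pattern | r = 1: slopes vs mixed | r = 2: slopes vs mixed |
|---|---|---|
| Complete | 85% vs 85% | 65% vs 66% |
| 10% leave per visit | 53% vs 70% | 28% vs 55% |
| 20% of visits missed at random | 83% vs 83% | 56% vs 62% |

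The average estimates were close to the true value under both methods. The difference is in precision.

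**The case against.** **The method is partly inferred.** No section says that a slope is computed per child and regressed unweighted. Terminology in 4.8 is loose: mixed models are attached to cross-sectional data, so linear models may not be meant to exclude them, and Aim 1 leaves them open. This stands. The supportable statement is that the plan is unspecified and that 4.7 and 4.8 need reconciling.

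**Missed visits are not the driver.** A reader might infer that any missed visit does damage, or that the child-dependent seventh visit does. Step 3 contradicts the first. The seventh visit is listed after month 36, so it does not create short series. Remote visits (section 4.1) drop the peg test and samples but may keep parts of FARS, questionnaires and timed walks, so they give mostly scattered gaps. The large losses need early departure, for which the documents give no rate.

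**FACOMS data shorten the argument.** Step 4 shows how much. This also stands, but only for shared measures (such as FARS, peg test, walks, ADL and PedsQL) in co-enrolled, consenting children. It does not help TUG, Berg, the biomarkers or children outside FACOMS.

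**No bias is shown.** A reader might infer that noisy slopes pull the estimates in one direction. Equal weighting inflates variance; nothing here shows a shifted estimate.

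**It is a secondary, non-confirmatory analysis.** True, but the plan itself calls these predictors part of its goal, and the remedy costs almost nothing.

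**Conclusion.** The concern holds as a matter of specification and efficiency. The plan names an unweighted-sounding method for predictors of change, without a rule for unequal follow-up, while leaving a better one optional for Aim 1.

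Without earlier data and with r between 1 and 2, the variance is about 1.55 to 2.7 times optimal with 10% and 10% of children on short follow-up, and about 1.9 to 3.75 times with 20% and 10%. It is about 1.1 to 1.2 times at r = 0.5, and close to 1 with complete data or scattered gaps. These sizes rest on assumed dropout, an assumed r and the inferred per-child slope; the documents fix none of them.

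Two stronger readings should be resisted. A mixed model does not by itself cure bias from timed walks that more severely affected children are not asked to do (section 5.6), if that depends on unobserved values. Nor does the argument extend to the responsiveness ratio in 4.7: its SD of change includes measurement error, and it should, because a model-based slope SD would make a noisy and a precise test look alike.

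**What to change.** In 4.7 and 4.8, replace the regression wording for rate of change with one linear mixed model per measure:
- random intercept and random slope for each child;
- actual visit time, using all visits, and a statement of whether earlier FACOMS visits enter;
- time × age, time × GAA repeat length and time × sex terms.

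For CrCEST (n = 12) and MEP (n = 30), allow in advance a simpler random-effects structure if the model does not converge. Leave the SD of change in the responsiveness ratio as it is; do not substitute the model-based slope SD.

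The cost is SAP wording and standard software, with no extra visits or tests. The downside is convergence checking in the small subsets. Walks omitted because of severity remain a separate missing-data question.

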4.8 Statistical Methods

Aim 1: Results will be summarized with standard descriptive statistics using parametric or non-parametric methods, as appropriate given the variable distributions. Each of the parameters tested here have been abnormal in FRDA patients previously, including children. However, the specific features of how they behave in large pediatric cohorts is unclear. Thus, the most important analyses will be how the tests behave over time and how they reflect disease severity. Data for test-retest for the first 5 subjects at the primary site will be evaluated by determining the coefficient of variation over the tests. This will be performed immediately after study initiation as a separate analysis to confirm that the initial protocols have sufficient reproducibility to be useful. Full data collection will then proceed. Data from measures that were repeated (timed walks, TUG, CCFS tests) will be analyzed as means of the repeated tests and test retest features between trials. CCFS values will be analyzed as each hand separately (dominant vs non dominant) and hands together. Each test will be assessed in regression or mixed linear models accounting for age, sex and GAA repeat length. In addition the change over time will be established as well as the reproducibility of that change.

Aim 2: Results will be summarized with standard descriptive statistics using parametric or non-parametric methods, as appropriate given the variable distributions. In this biochemical aim, the major analysis will examine the relationship of frataxin levels and downstream biomarkers with disease progression. This will be performed in 2 ways. First using cross sectional data, we will construct mixed linear models that allow the assessment of their relationship of marker values (frataxin, 13C metabolite levels, Apo A1) to age, GAA repeat length and sex. Secondly, we will assess the change in values over time both in absolute value and percent change to understand the overall meaning of results. In addition, the change over time will be examined in relation to age, sex, and GAA repeat length in linear models. We will also examine the levels of each marker at baseline with the change in clinical measures from aim 1. This will allow us to understand the degree to which clinical change reflects individual biochemical events and whether clinical and biochemical events correlate temporally. This analysis will be supplemented by analysis assessing whether the change in levels of the biomarkers predicts clinical change.

Aim 3. Each of the measures here (MEP, CrCEST) has differentiated FRDA subjects from controls in previous studies. For this proposal though, the crucial analyses should ascertain the relationship between physiological values from CrCEST and MEP and disease status from clinical measures. Results will be summarized with standard descriptive statistics using parametric or non-parametric methods, as appropriate given the variable distributions. In cross sectional analyses, results from each of the outcome measures (frataxin levels, platelet metabolic markers, ApoA-1, and recovery time from CrCEST) will

be used as dependent variables in multiple linear regression models or mixed models examining the independent effects of age, GAA repeat length and sex as dependent variables. This will allow us to define the degree to which each outcome marker is predicted by genetic severity (GAA repeat length), disease progression (age) or both. We will also directly correlate results between MEP and CrCEST to ascertain the degree to which they reflect the same construct (FRDA disease progression). Finally, we will examine correlations and regression modelling between physiological results and clinical measures (Aim 1) and frataxin levels (Aim 2)

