3.1.2 Assessment Phase

Visit 1 (0 months) Subjects will be assessed by medical history, neurological tests (FARS, Timed 25 foot walk (T25W), Timed 1 and 6 minute walks, Timed up and go (TUG), Berg Balance scale (BBS), 9 hole peg test (9HPT), PedsQL, ADL score and ataxia disability scale), biochemical tests (frataxin level, platelet metabolic biomarkers), and physiological testing (CrCEST, MEP). Data will be collected over a one day visit.

Visit 2. (6 months) Subjects will be assessed by medical history, neurological tests (FARS, Timed 25 foot walk (T25W), Timed 1 and 6 minute walks, TUG, BBS, 9HPT, PedsQL, ADL score, ataxia disability scale), and biochemical tests (frataxin level, platelet metabolic biomarkers). Data will be collected over a one day visit.

Visit 3 (12 months) Subjects will be assessed by medical history, neurological tests (FARS, Timed 25 foot walk (T25W), Timed 1 and 6 minute walks, Timed up and go (TUG), Berg Balance scale (BBS), 9 hole peg test (9HPT), PedsQL, ADL score and ataxia disability scale), biochemical tests (frataxin level, platelet metabolic biomarkers), and physiological testing (CrCEST, MEP). Data will be collected over a one day visit.

Visit 4. (18 months) Subjects will be assessed by medical history, neurological tests (FARS, Timed 25 foot walk (T25W), Timed 1 and 6 minute walks, TUG, BBS, 9HPT, PedsQL, ADL score, ataxia disability scale), and biochemical tests (frataxin level, platelet metabolic biomarkers). Data will be collected over a one day visit.

Visit 5 (24 months) Subjects will be assessed by medical history, neurological tests (FARS, Timed 25 foot walk (T25W), Timed 1 and 6 minute walks, Timed up and go (TUG), Berg Balance scale (BBS), 9 hole peg test (9HPT), PedsQL, ADL score and ataxia disability scale), biochemical tests (frataxin level, platelet metabolic biomarkers), and physiological testing (CrCEST, MEP). Data will be collected over a one day visit.

Visit 6 (36 months) Subjects will be assessed by medical history, neurological tests (FARS, Timed 25 foot walk (T25W), Timed 1 and 6 minute walks, Timed up and go (TUG), Berg Balance scale (BBS), 9 hole peg test (9HPT), PedsQL, ADL score and ataxia disability scale), biochemical tests (frataxin level, platelet metabolic biomarkers), and physiological testing (CrCEST, MEP). Data will be collected over a one day visit.

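### Averaging individual percent changes in the Aim 2 markers overstates change by about CV²; a log-scale mixed model over all visits avoids this at little cost

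*Combined protocol and SAP*

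**What the plan says.** Section 4.7 sets the Aim 2 endpoint without naming a scale: "The rate of change of frataxin and each platelet biomarker will be determined as primary endpoints". Section 4.8 (Aim 2) then names two scales side by side: "we will assess the change in values over time both in absolute value and percent change to understand the overall meaning of results". It does not rank them, define the denominator of percent change, or mention a log scale.

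Summaries are left open, "using parametric or non-parametric methods, as appropriate given the variable distributions". For the covariate analysis, "the change over time will be examined in relation to age, sex, and GAA repeat length in linear models", without saying which scale of change is the response.

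On the baseline value, Section 3.1.2 lists one set of "biochemical tests (frataxin level, platelet metabolic biomarkers") at Visit 1. Averaging of repeats is described under Aim 1 only: "Data from measures that were repeated (timed walks, TUG, CCFS tests) will be analyzed as means of the repeated tests". A single baseline reading as denominator is therefore an inference, but the natural one.

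**The concern.** Dividing by one error-prone reading is not neutral. A baseline that happens to read low inflates the percent change by more than an equally high reading deflates it, so the average of individual percent changes is pushed upward even when nothing has changed. The push is already present at the first follow-up and depends on measurement noise, not on the disease.

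Two uses are exposed: a mean of individual percent changes, and a linear model with percent change as the response, because such a model also estimates arithmetic means. The direction matters. Section 1.1 foresees frataxin level as a main biochemical endpoint for therapies meant to raise it, so an upward artefact in natural history data would point the same way as the treatment effect those trials look for. Section 4.7 also wants to identify the markers most sensitive to progression. If they are compared on percent change, each marker carries its own bias, set by its own noise.

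**Working it through.** **Inputs.** The documents give no figure to reproduce.
- Within-child CV of frataxin or the platelet markers: not given. The only mention of a coefficient of variation is under Aim 1, without a value: "Data for test-retest for the first 5 subjects at the primary site will be evaluated by determining the coefficient of variation over the tests". Assumed 10%, 20% and 30%.
- True relative decline *d*: not given, since "the goal is to define how each of the tests change over time in children with FRDA". Assumed 0% and 5%.
- Visit times: 0, 6, 12, 18, 24 and 36 months (Section 3.1.2).
- Sample size: 110 (Section 4.9).

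**Two-reading contrast.** Let the true level be T at baseline and T(1 − d) at follow-up. Each reading carries an independent lognormal error with mean 1 and log-variance s² = ln(1 + CV²). Then

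E[Y1/Y0] = (1 − d) · exp(s²) = (1 − d)(1 + CV²).

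With d = 0 the bias is 100 · CV² percentage points. The expected change is positive despite a true decline only if d < CV²/(1 + CV²).

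| CV | Mean percent change, d = 0 | Mean percent change, d = 5% | Largest decline that can change sign |
|---|---|---|---|
| 10% | +1.0 | 0.95 × 1.01 − 1 = −4.05% | 0.01/1.01 = 0.99% |
| 20% | +4.0 | 0.95 × 1.04 − 1 = −1.2% | 0.04/1.04 = 3.85% |
| 30% | +9.0 | 0.95 × 1.09 − 1 = +3.55% | 0.09/1.09 = 8.26% |

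**Other summaries.** A simulation of 2,000,000 children per setting gave, for a true 5% decline at CV 20%: mean percent change −1.2%; median percent change, ratio of means and back-transformed mean log ratio all −5.0%. At CV 30% the mean percent change was +3.6% (closed form +3.55%) and the other three again −5.0%. The ratio of means uses mean absolute change, so the absolute scale is free of this bias.

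**Samples of 110.** In 20,000 simulated studies per setting, with complete data, one follow-up contrast and no true change, a mean percent rise with t > 1.98 (nominal rate 2.5%) occurred in about 10%, 27% and 50% of studies at CV 10%, 20% and 30%. With a true 5% decline the mean percent change was above zero in 0.1%, 33% and 79%.

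**As a rate.** The endpoint is a rate, so the bias should also be put per year. Suppose percent change from baseline enters a least-squares slope over all listed visits, with baseline fixed at zero. In years, the times are 0, 0.5, 1, 1.5, 2 and 3.
- Mean time = 8/6 = 1.333.
- Sum of squares about the mean = 16.5 − 6 × 1.333² = 5.833.
- With no true change, every follow-up has expectation CV² and baseline has 0, so the slope bias is (1.333/5.833) · CV² = 0.23 · CV² per year.

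This gives +0.2, +0.9 and +2.1 percentage points per year at CV 10%, 20% and 30%. It assumes complete visits and independent errors.

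**The case against.** The strongest reply is that the plan does not rest on percent change. The same sentence also plans absolute change, the endpoint in Section 4.7 names no percent scale, and the median, which Section 4.8 permits, is unbiased in this model. All of that stands: a spurious percent rise would sit beside an unbiased absolute result. What the reply does not remove is that percent change is a planned analysis, that nothing says what to conclude if the two scales disagree, and that the linear models would take in the bias if percent change were their response.

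It is also fair that the size rests on assumed CVs and on independent errors. Error shared between a child's samples, for instance samples assayed together, would partly cancel in the ratio and shrink the bias. The documents settle neither point. And the larger figures belong to a two-reading contrast; as a yearly slope the bias is about a quarter of that.

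A reader might infer three stronger things that the documents do not support:
- **That neither stated scale is usable.** Absolute change depends on the starting level only if decline is proportional, which is not stated, and even then mean absolute change over mean baseline recovers the relative change.
- **That a false association with GAA length will appear.** This needs noise that differs by frataxin level, percent change as the model response and a mean-based fit. The documents establish none of these.
- **That a true frataxin decline is likely to read as a rise.** With a 5% decline the expected contrast stays negative at CV 20% and reverses only at the higher assumed noise.

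**Conclusion.** The concern holds in a limited form. Individual percent change from what appears to be a single baseline reading is biased upward by about CV² when averaged or modelled linearly. Under independent multiplicative error, and for assumed CVs of 10% to 30%, that is +1 to +9 points per contrast, or about +0.2 to +2.1 points per year as a slope over 0 to 36 months. Sign reversal is possible in a two-reading contrast, but only for declines below CV²/(1 + CV²). Absolute change and the median percent change are unaffected, so the Aim 2 endpoint as a whole is not undermined. Confidence is high in the algebra and moderate in its practical weight, because the documents give neither the noise nor the expected decline. This is a cheap improvement.

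**What to change.** In Section 4.8 (Aim 2), replace individual percent change with a mixed model of log(marker) on time using all visits. Report the slope back-transformed to percent per year with a 95% CI, and use this scale whenever relative change is related to age, sex and GAA length. Keep absolute change alongside it.

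The cost is a sentence or two and no new data. The downside is that a log cannot take zeros, so Section 4.8 must also state how values at zero or below the detection limit are handled. The back-transformed slope also summarises progression as a constant relative rate, which is a further reason to keep the absolute scale in view.
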